8.2.3 Secondary analysis

Secondary outcome data will be summarised descriptively at each time point, overall and by trial arm. The secondary outcomes will be analysed either by comparing trial arms at week 6 using ANCOVA models adjusting for baseline scores, or by employing mixed effects models for repeated measurements (MMRMs). The baseline scores, treatment group, time point, and treatment group by timepoint interaction terms will be included as covariates. A random effect for participant will be used to account for repeated measurements within participants over time. This will allow efficient use of the data collected, and account for potential within patient correlation.

Further analysis with regards specific FAPD subgroup and ethnicity will also be undertaken and will be described in full in the formal statistical analysis plan [32,33].

ENT08UK Clinical Investigation Plan v1_07/05/2025

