The screening clinic appointment will take place within a routine clinic visit which may be on site or remote. Recruitment during a remote clinic call will only occur where the child has already been clinically assessed and examined by the referring paediatrician. Children previously diagnosed with a FAPD can be considered for invitation to join the study without the need for an additional routine clinic visit. Patients and their parent/carer that have a clinician's confirmed diagnosis with specific FAPD category (H2a, H2b, H2c or H2d) and deemed eligible to join the study will receive patient information sheets and a pregnancy test kit for those eligible. After 24 hours consideration the Research Nurse will call and book a remote recruitment

appointment or an additional clinic visit. The research nurse will recruit and consent patients during the recruitment appointment for a 2week observational phase.

Eligible patients at baseline will be randomised 1:1 to receive Enterosgel® or placebo for 4 weeks during the double-blind treatment phase (weeks 3-6), then all patients will receive open-label Enterosgel® treatment for a further 4 weeks (weeks 7-10). Patients will take a dose in the morning and evening, with an increase in dose from 53% to 80% of the recommended daily dose for diarrhoea at week 3-4 (including in the placebo arm). The purpose of the dose adjustment is two-fold; first, it will maximise the efficacy of the active treatment by making a step-wise increase in dose and second, it will provide us with data to help define the optimal dosage regimen(s) for Enterosgel®.

After the double-blind treatment phase, all patients will receive open-label Enterosgel® treatment for 4 weeks. As in the double-blind phase, patients will take an increase in dose from 53% to 80% of the recommended daily dose for diarrhoea at week 3-4. As the treatment will be open-label, this is a pragmatic part of the trial, allowing us to better understand the optimal dosage regimen(s) for Enterosgel®. After 4 weeks of open-label treatment, the patients will return to standard care.

The study outcomes align with the 8 core outcome set for FAPDs in children as outlined by articles listed on the COMET Core Outcome Measures in Effectiveness Trials database [22].

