3.2.2 Secondary Outcome Measures

3.2.2.1 Double-blind and Open-label treatment phase

The secondary outcome measures in the Enterosgel® versus the placebo arm during the double-blind and open-label treatment phase are listed in **Table 1**.

Table 1. Secondary outcome measures for the double-blind and open-label treatment phase

Outcome Measure	Time points and method of assessment	Definition
1. Abdominal pain score	Daily diary	Mean daily Wong-Baker FACES Pain Rating Scale
2. Frequency of abdominal pain	Daily diary	Proportion of days with any abdominal pain
3. Days missed nursery/school	Daily diary	Proportion of days missed nursery/school
4. Change in the Stomach Pain and Hurt total score	Baseline, weeks 6 and 10 (PedsQL 3.0 GIS module; comprised of 6 items)	Parent/carer proxy-report for 3-4-year-olds and child self-report from 5-18 years; by parent/carer proxy-report for 3-18-year-olds)
5. Change in individual components of the PedsQL 3.0 GIS module	Baseline, week 6, 10 (PedsQL 3.0 GIS module)	Parent/carer proxy-report for 3-4-year-olds and child self-report from 5-18 years; by parent/carer proxy-report for 3-18 years old. Individual components of the PedsQL 3.0 GIS module: stomach discomfort when eating (5 items), food and drink limits (6), trouble swallowing (3), heartburn and reflux (4), nausea and vomiting (4), gas and bloating (7), constipation (14), blood in bowel movement (2), diarrhoea (7), worry about bowel movements (5), medicines (4), communication (5).
6. Change in total PedsQL 3.0 GIS module score	Baseline, week 6,10 (PedsQL 3.0 GIS module)	Parent/carer proxy-report for 3-4-year-olds and child self-report from 5-18 years; by parent/carer proxy-report for 3-18 years old.
7. Change in health-related quality of life KIDSCREEN- 27 questionnaire	Baseline, week 6, 10 (Health-related quality of life KIDSCREEN-27)	Total Health-related quality of life KIDSCREEN- 27 score (parent reported 3-7 years, child self- report 8-18 years)
8. Change in health-related quality of life KIDSCREEN-27 questionnaire "General Mood and Feelings about Yourself" sub- score	Baseline, week 6, 10 (Health-related quality of life KIDSCREEN-27)	Health-related quality of life KIDSCREEN-27 sub-score for "General Mood and Feelings about Yourself" (7 questions; parent reported 3-7 years, child self-report 8-18 years)
9. Acceptability of the study interventions	Daily (diary)	Compliance with taking study intervention each day*

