5.1.1.2 Open-label phase

For the open-label treatment phase, all patients will receive Enterosgel® daily for 4 weeks in standard 225g tubes, which are identical to those available over-the-counter in the UK.

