8. STATISTICS

8.1 SAMPLE SIZE CALCULATION

In a previous clinical trial of Mebeverine in the treatment of FAPD in children [30], the mean (SD) change from baseline in the Wong-Baker FACES Pain Rating Scale in the placebo arm was -1.2 (1.5). We consider that a 1-point larger reduction in the Enterosgel arm (a mean change from baseline of -2.2) would be clinically significant. The number of patients required to observe this difference with 80% power and α =0.05 is approximately n=130 (or n=65 per arm). We would increase the sample size to n=154 (77 per arm) to allow for 15% drop-outs.

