8.2 STATISTICAL ANALYSES

This trial will be reported according to the CONSORT guidelines for clinical trials (Consolidated Standards Of Reporting Trials statement (http://www.consort-statement.org/) [31]. Primary data analyses will be based on the intention-to-treat principle. The per-protocol analyses will include children with 80% or greater treatment compliance. Recruitment and attrition rates will be calculated as percentages with 95% CIs. Percentage of patients completing the protocol will be reported and reasons for deviations/study withdrawal collected. Data will inform a power calculation for a definitive clinical and cost-effectiveness study. Descriptive sub analyses, if numbers allow, will be made based on specific FGID diagnoses.

All statistical analyses will be described in detail in the Statistical Analysis Plan.

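### The repeated-measures model for secondary outcomes names only a participant random effect; read literally, it assumes equal variance at weeks 6 and 10 and can misstate the week 6 standard error

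*Protocol*

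**What the plan says.** Section 8.2.3 of the protocol gives two routes for secondary outcomes: "by comparing trial arms at week 6 using ANCOVA models adjusting for baseline scores, or by employing mixed effects models for repeated measurements (MMRMs"). For the second route it lists the fixed effects: "The baseline scores, treatment group, time point, and treatment group by timepoint interaction terms will be included as covariates". It then says how the repeated values are to be handled: "A random effect for participant will be used to account for repeated measurements within participants over time". No other covariance term, residual structure or type of standard error is mentioned.

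In Table 1 (section 3.2.2.1) the PedsQL and KIDSCREEN outcomes are measured at baseline, week 6 and week 10. With baseline as a covariate, two repeated values remain. They come from different treatment conditions. Week 6 closes the blinded two-arm phase. Of what follows, section 3.1 says "then all patients will receive open-label Enterosgel® treatment for a further 4 weeks (weeks 7-10"; section 5.1.1.2 agrees.

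Section 8.2 adds: "All statistical analyses will be described in detail in the Statistical Analysis Plan". That plan is not at hand.

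**The concern.** An MMRM in the usual sense gives each visit its own variance. A participant random effect with ordinary residuals does not. It gives one variance for all visits and one correlation (compound symmetry). With a single baseline term, the slope on baseline is also shared by both visits.

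The protocol gives no reason to expect equal spread at the two visits. At week 10 all children have had four weeks of open-label active treatment. The PedsQL asks about the past month (section 6.3.2), so its week 6 and week 10 scores cover different treatment phases. If the spread changes, the week 6 arm difference gets an error bar built partly from week 10 data.

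This difference is the blinded efficacy comparison for the questionnaire outcomes. If the spread falls by week 10, its confidence interval is too narrow and the test rejects too often. If the spread rises, the interval is too wide and power is lost.

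**Working it through.** The protocol states no figure to reproduce here. It gives no SD for any questionnaire outcome at week 6 or week 10, so r = SD10/SD6 is an assumption and is varied. The SDs meant are those left after adjustment for baseline, not SDs of raw scores.

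**Inputs.** Two post-baseline visits (Table 1). Evaluable sample of 65 per arm (section 8.1: "approximately n=130 (or n=65 per arm")). Complete data, no true arm difference, two-sided 5% test.

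**Step 1: standard errors.** With n per arm, the true standard error of the week 6 arm difference is sqrt(2·SD6²/n). A random-intercept model with one residual variance estimates a single marginal variance, which with two complete visits is close to the average, (SD6² + SD10²)/2 = SD6²·(1+r²)/2. Its week 6 standard error is therefore sqrt(2·SD6²·(1+r²)/(2n)).

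**Step 2: ratio.** Model SE / true SE = sqrt((1+r²)/2). The sample size cancels.

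**Step 3: type I error.** This is 2·(1 − Φ(1.96 × ratio)).

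- r=0.8: sqrt((1+0.64)/2) = sqrt(0.82) = 0.906; 1.96 × 0.906 = 1.775; type I error 7.6%.
- r=1.25: sqrt((1+1.5625)/2) = sqrt(1.28125) = 1.132; 1.96 × 1.132 = 2.219; type I error 2.7%.

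| Assumed r | Model SE / true SE | Type I error |
|---|---|---|
| 0.7 | 0.863 | 9.1% |
| 0.8 | 0.906 | 7.6% |
| 0.9 | 0.951 | 6.2% |
| 1.0 | 1.000 | 5.0% |
| 1.1 | 1.051 | 3.9% |
| 1.2 | 1.105 | 3.0% |
| 1.25 | 1.132 | 2.7% |
| 1.3 | 1.160 | 2.3% |

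**Step 4: simulation.** A Monte Carlo check with the pooled-variance standard error (65 per arm, correlation 0.5, 20,000 runs per setting) gave 9.4%, 7.5%, 5.1%, 3.3% and 2.4% at r = 0.7, 0.8, 1.0, 1.2 and 1.3. Random-intercept models fitted by REML (800 runs each) gave 10.8%, 6.5% and 5.8% at r = 0.7, 0.8 and 1.0. Week 6 ANCOVA on the same data gave 4.3% to 5.8%. A separate set of 1,200 fitted trials per setting gave 7.3%, 6.2% and 2.8% at r = 0.8, 1.0 and 1.25, with ANCOVA at 4.6%, 6.0% and 5.0%. Near a 5% rate the simulation error is about 0.8 percentage points for 800 runs and 0.6 for 1,200. The fitted models agree with the formula within that noise.

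**Step 5: does the repair work?** An unstructured model was not simulated separately; the argument is algebraic. With complete data and a baseline-by-time-point term, both visits have the same regressors. The week 6 arm difference then equals the week 6 ANCOVA estimate and uses the week 6 variance, so the nominal rate is 5%.

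**The case against.** The strongest reply is that the protocol never says the participant effect is the only covariance term. It is silent on the residual structure, and a participant effect can be combined with visit-specific residual variances or robust standard errors. Covariance structure is commonly settled in the statistical analysis plan, to which section 8.2 defers. This stands in part. A reader might infer that the protocol imposes equal variances and that its week 6 standard errors are wrong. The text supports neither: the first is a literal reading of an incomplete specification, and the second depends on an unknown r. What remains is that section 8.2.3 does name a structure, and an analysis plan that follows it word for word inherits the assumption.

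Second, the same sentence offers week 6 ANCOVA, and section 8.2.2 says secondary continuous outcomes will be handled much like the primary. ANCOVA is not affected. This stands and limits the point. It does not remove it: ANCOVA is offered only for week 6, while Table 1 lists these outcomes for both phases, so the mixed model may well be used. When variances differ, the two permitted routes also have different error rates for the same contrast.

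Third, the direction is unknown. A floor effect in raw scores does not translate directly into a given r, because r refers to baseline-adjusted SDs. With r between 0.9 and 1.1 the rate moves only between 6.2% and 3.9%. This stands.

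Fourth, the shared baseline slope does not bias the arm difference, because arms are randomised. This stands; no size is claimed for it.

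**Conclusion.** The point holds as a minor one, confined to secondary outcomes with two post-baseline values and only if the mixed-model route is taken literally. It rests on independent equal-variance residuals, complete data and an assumed r. The week 6 standard error would then be about 9% too small at r=0.8 and 13% too large at r=1.25; if the two spreads are equal, nothing is wrong.

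A reader might go further and conclude that the trial's efficacy result is at risk. The protocol does not support that: the primary outcome is analysed by ANCOVA (section 8.2.2) and is untouched. The case for acting is that the literal model carries an avoidable assumption, its MMRM label and its random-effect wording do not match, and the repair is close to free.

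**What to change.** In section 8.2.3, and in the statistical analysis plan, replace the random-effect sentence with wording along these lines:

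*For outcomes with two post-baseline values (PedsQL and KIDSCREEN at weeks 6 and 10, and diary outcomes summarised as one value per treatment phase), the model will use an unstructured covariance matrix across the two post-baseline time points, a baseline-by-time-point interaction and Kenward-Roger degrees of freedom. The double-blind arm difference will be read from this model.*

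The restriction to two values matters. An unstructured matrix over the eight post-baseline diary weeks has 8×9/2 = 36 parameters. Over 56 daily records it has 56×57/2 = 1,596, against 154 children. It should not be used for daily or weekly diary records.

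The cost is one sentence in each document and one extra covariance parameter (three instead of two). No data or patients are added. The change should be made before unblinding, so that the covariance is not chosen after the results are seen.

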8.2.4 Handling of missing data

Where appropriate, multiple imputation will be used to impute missing values under a missing at random assumption in order to avoid excluding patients from the analysis. Multiple imputation involves creating multiple copies of the data set, with the missing values replaced by imputed values drawn from their predicted distribution by using the observed data [24].

8.3 ANALYSIS POPULATIONS

8.3.1 Intention-to-treat population (ITT)

ITT population will include all randomised patients analysed in the groups to which they were randomised to, regardless of whether they received or adhered to the allocated intervention.

8.3.2 Per-protocol population (PP)

PP population will include all patients who completed the study without reported protocol violations and with with 80% or greater treatment compliance.

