2.2 OBJECTIVES

2.2.1 Primary objective

The primary objective of this study is to test the efficacy (superiority) of Enterosgel® (Bioline Products s.r.o, Czech Republic) compared with placebo in terms of change in mean abdominal pain score as recorded in the daily diary between the initial observation phase (weeks 1-2) and the double-blind treatment phase (weeks 3-6).

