3.3 DEFINITION OF END OF TRIAL

End of trial is defined as the last follow-up appointment for the last patient. Patients with unresolved SAEs at the last follow-up appointment would be followed up until SAE resolution or stabilisation.

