6.2 STUDY VISITS AND PROCEDURES

Participants will attend one screening study visit during a routine clinic visit (on site or remote) at the recruiting site followed by a remote Recruitment visit. Informed consent and assent (written or e-consent) will be obtained by the research nurse before any study procedures are conducted. Participants who pass the diagnostic criteria and consent to proceed will be entered into the study. Demographic and clinical data will be collected and questionnaires completed at the recruitment visit and participants entered into the observational phase. Further appointments/calls will be conducted by the research team; at baseline (week 3), week 4 and at the end of the double-blind phase (week 8) and end of the open label phase (week 10).

The schedule of appointments and procedures conducted at each visit are summarised in **Table 3** and described in more detail below. +/- 1 week is allowed around each follow-up appointment. **Table 4** summarises the schedule for completion of study diary and questionnaires. All remote appointments and follow-up calls, can be conducted either via telephone or video call, depending on the participant's preference. At the end of the study (week 10), children will continue under the care of their paediatrician usually including a routine follow-up clinic at week 12 (3 months from the initial screening visit).

Procedure	Screening appointment (Recruitment site/remote)	Recruitment appointment (remote)	Baseline appointment (remote) Week 3	Complian ce call Week 4	Follow-up 1 appointment (remote) 6 weeks	Follow-up 2 appointment (remote)10 weeks
	0 weeks					
Informed consent		Х				
Patient screening	Х					
Demographic information	x					
Review of medical history and concomitant medications	Х					
Pregnancy test where needed			x			
Instructions on completion of diary		x	x		X	
Confirming eligibility (based on patient diary data; review of medical notes; pregnancy test)			X			
Randomisation			Х			
Instructions on use of study treatment			X		X	

Table 3. Schedule of events and appointment procedures.

Review of changes in medical history or concomitant medications		Х		Х	Х
Adverse Events			х	Х	Х
Checking compliance to study procedures and advising on any issues			Х		
Adequate relief question				Х	Х

Table 4. Study diary and questionnaire completion schedule. "X" means that the item is completed once that week, except where otherwise specified.

Visit/study period	Week	Diary*	PedsQL-3.0-GIS	KIDSCREEN

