		-		
Recruitment appointment	0		Х	Х
Observation phase	1	X (daily)		
	2	X (daily)		
Blinded treatment period	3	X (daily)		
	4	X (daily)		
	5	X (daily)		
Follow-up 1 appointment	6	X (daily)	Х	Х
Open-label treatment period	7	X (daily)		
	8	X (daily)		
	9	X (daily)		
Follow-up 2 appointment	10	X (daily)	Х	Х

*The daily diary will collect information for the Wong-Baker FACES Pain Rating Scale for 10 weeks and study compliance for 8 weeks (weeks 3-10)

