10.2 PROTOCOL DEVIATIONS AND VIOLATIONS

A protocol deviation is any noncompliance with the clinical trial protocol or GCP. The noncompliance may be either on the part of the participant, the investigator, or the study site staff.

Protocol violations are significant deviations that reduce the quality or completeness of the data, make the Informed Consent Form inaccurate, or impact a subject's safety, rights, or welfare [34].

Examples of protocol violations relevant to this study may include the following:

- 1. Inadequate or delinquent informed consent
- 2. Inclusion/exclusion criteria not met
- 3. Unreported SAEs

- 4. Materially inadequate record keeping
- 5. Intentional deviation from the protocol, GCP, or regulations by study personnel
- 6. Subject repeated non-compliance with study requirements
- 7. Dispensing of incorrect treatment
- 8. Not using any study treatment
- 9. Starting on antidepressants, intestinal adsorbents, strong opioids or probiotic supplements
- 10. Initiating any new treatment during the study that might have a significant impact on abdominal pain, according to the PI's opinion

All deviations/violations must be addressed in study source documents and reported to the Sponsor and the HRA and/or the MHRA as per their guidelines. All protocol violations should be recorded in the Protocol Violation eCRF. The site PI/study staff is responsible for knowing and adhering to these requirements. As a result of deviations and violations, corrective actions are to be developed by the Sponsor and/or site as appropriate and implemented promptly.

Participants with protocol violations will be excluded from the PP population.

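### The only per-protocol set is defined over the whole 10-week study, so events in open-label weeks 7-10 can remove a child with complete double-blind data from the PP comparison of weeks 3-6

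*Protocol*

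**What the plan says.** Five parts of the protocol bear on this.

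- **PP set.** Section 8.3.2 reads "PP population will include all patients who completed the study without reported protocol violations" and adds a threshold of 80% or more treatment compliance. Section 8.2 mentions the compliance threshold alone. No second PP set is defined.
- **End of the study for a child.** Section 6.2: "At the end of the study (week 10), children will continue under the care of their paediatrician".
- **Violations.** Section 10.2 closes with "Participants with protocol violations will be excluded from the PP population". Its examples include starting antidepressants or probiotics, repeated non-compliance, and "Initiating any new treatment during the study that might have a significant impact on abdominal pain". No period is attached to any of them.
- **Compliance recording.** The footnote to Table 4 in section 6.2 says the diary collects "study compliance for 8 weeks (weeks 3-10"), so both treatment phases are covered. The period over which the 80% is calculated is not given.
- **Endpoint and switch.** The primary objective (section 2.2.1) concerns the change "between the initial observation phase (weeks 1-2) and the double-blind treatment phase (weeks 3-6"). Section 3.1 then states: "then all patients will receive open-label Enterosgel® treatment for a further 4 weeks (weeks 7-10").

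Section 8.2 bases the primary analyses on intention to treat.

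**The concern.** A per-protocol set for a comparison should be fixed by what happens up to the end of that comparison. Here it is also fixed by the four weeks that follow, when both arms take the same known product.

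This has two consequences. Children whose blinded data are complete and compliant can be discarded for reasons unrelated to weeks 3-6. Also, the arms reach the switch with different histories: one has just finished placebo and meets Enterosgel for the first time, and the other continues it. Leaving or starting another treatment in weeks 7-10 may therefore depend on arm and on the response already observed. Conditioning the week 3-6 comparison on such events can introduce selection that randomisation does not remove.

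At stake is the usefulness of the PP analysis as a supportive result. The primary ITT result is not at stake.

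**Working it through.** The plan gives no figure for this point, so the first two steps set the rules against the timeline. The last two are arithmetic.

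**Step 1. Periods covered by each rule.**
- Primary comparison: weeks 1-2 against weeks 3-6 (section 2.2.1).
- PP completion: to week 10 (section 8.3.2 read with section 6.2).
- PP violations: no limit, so to week 10 (section 10.2).
- PP compliance: period not stated; recorded in weeks 3-10 (Table 4 footnote).

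The completion and violation rules both run four weeks past the endpoint.

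**Step 2. Children with complete, fully compliant data for weeks 3-6.**
- Withdraws in week 8: did not complete the study, so out of PP.
- Starts a probiotic or antidepressant in week 9: a listed example of a violation, so out of PP.
- Needs a slow-release medicine in week 8: section 5.3.1 calls for withdrawal, so out of PP.
- Stops open-label Enterosgel in week 7 but stays in follow-up: section 4.4 records a deviation, and only violations exclude. This child leaves PP only if the lapse is classed as repeated non-compliance or the compliance figure falls below 80%.

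**Step 3. Compliance if pooled over both phases.** Assumption: equal weight per dose, two doses a day.
- Scheduled doses: 28 × 2 = 56 per phase, 112 in all. Threshold: 0.80 × 112 = 89.6.
- All 56 blinded doses taken: open-label doses needed = 89.6 − 56 = 33.6, and 33.6 / 56 = 60%. Below 60% open-label compliance the child fails.
- 60% blinded and 100% open-label: (0.60 × 56 + 56) / 112 = 89.6 / 112 = 80%. The child passes.
- 100% blinded and 79% open-label: (100 + 79) / 2 = 89.5%. The child passes.

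A pooled rule can therefore drop a child who adhered fully to blinded treatment and keep one who did not. If the 80% is instead taken over weeks 3-6 only, neither happens.

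**Step 4. Illustration of lost precision.** The protocol gives no open-label attrition or violation rate. Assumption: 5, 10, 15 or 20% of 130 children with evaluable blinded data leave PP solely because of weeks 7-10.
- Remaining: 123.5, 117, 110.5 or 104.
- Power for a 1-point difference, two-sided 0.05, with n per arm: Φ(1 / (SD × √(2/n)) − 1.96).
- SD 1.5 (section 8.1): 0.967 with no loss, then 0.959, 0.950, 0.939 and 0.925.
- SD 2.03: 0.802 with no loss, then 0.781, 0.759, 0.735 and 0.709.

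The second SD is shown because the inputs in section 8.1 do not reproduce its 65 per arm: 2 × (1.96 + 0.84)² × 1.5² / 1² gives 36 per arm, and 65 needs an SD of about 2.02. That is a separate matter and does not affect this point.

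**The case against.** The strongest reply concerns weight. This is a superiority trial with an ITT primary analysis, and nothing in the protocol makes a decision depend on PP. Nor does it say outright that PP is applied to the week 3-6 outcome. Completion to week 10 would be a sensible requirement for the open-label objectives, and section 8.2 leaves analysis detail to the SAP. This limits the importance of the point but does not remove it. Section 8.2 introduces the per-protocol analyses directly after the primary ones, so applying PP to the primary outcome is the natural reading. The protocol also states a rule here: an SAP with a week-6 set would contradict sections 8.3.2 and 10.2.

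It may be said that the study could mean the double-blind phase. Section 6.2 places its end at week 10. Section 3.3 ("End of trial is defined as the last follow-up appointment for the last patient") concerns the trial as a whole and does not settle when an individual child has completed.

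Three stronger readings are tempting, and the documents do not support them.
- **That falling below 80% in weeks 7-10 removes a child.** No per-phase threshold is stated, and Step 3 shows that 79% open-label compliance would pass a pooled rule. The footnote to Table 1 also says that pauses for constipation do not count as non-compliance.
- **That stopping open-label treatment by itself removes a child.** Section 4.4 makes this a deviation, with follow-up allowed to continue.
- **That the bias favours Enterosgel because its non-responders leave at the switch.** Nothing in the protocol reveals the blinded allocation at week 6, and section 6.4 limits unblinding to medical need. A child who did not improve may suppose that the blinded product was placebo and stay for the active one. If non-responders leave both arms equally, the difference shifts by about zero.

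**Conclusion.** The point holds as a defect in a stated definition. Completion and freedom from violations are required through week 10 for a comparison that ends at week 6, and the compliance threshold has no period. PP membership therefore depends on events after the endpoint, which loses valid blinded data and can introduce selection.

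Neither the direction nor the size can be determined from the protocol. The power figures above rest on assumed loss rates. A shift of 0.29 points in the PP mean can be computed if the worst-responding 10% of the Enterosgel arm all leave and no placebo child does (0.195 × SD 1.5), but that one-arm scenario has no basis in the documents and should not be read as an estimate. The same applies to a loss of about 12 children (7.5% of 154), which assigns half of the planned 15% drop-out to the period after week 6.

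The conclusion assumes that PP is applied to the double-blind comparison and that section 6.2 defines the end of the study for a child. The ITT primary analysis is unaffected, so this should be corrected but does not threaten the trial's main result.

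**What to change.** In section 8.3.2, define the PP set for the double-blind comparison as children who completed the double-blind phase to Follow-up 1, had no protocol violation up to that visit, and had at least 80% compliance with blinded treatment in weeks 3-6. If a PP analysis of the open-label phase is wanted, define a separate set for weeks 7-10. Limit the last sentence of section 10.2 in the same way, and carry the definitions into the SAP. State the weeks explicitly, because one sentence in section 6.2 puts the end of the double-blind phase at week 8 while the rest of the protocol puts it at week 6.

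The cost is a few sentences and possibly a second set to maintain. Compliance is already recorded daily. The protocol names a Protocol Violation eCRF but does not say that it captures dates, so the timing of each violation must be confirmed as available from that form.
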